5.2 Inclusion Criteria

- 1) Men and women aged between 18 and 50 years
- 2) eGFR (CKD-EPI) ≥ 45 ml/min/1,73 m2
- 3) Genetic Diagnosis of Type I ADPKD truncating mutation
- 4) Signed and dated informed consent

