12. STATISTICAL CONSIDERATIONS

12.1 Sample Size Determination and Rationale

In TEMPO 3:4, tolvaptan reduced the decline in eGFR from 3.70 to 2.72 ml/min per 1.73 m² per year (26.5%); P=0.001). A post hoc analysis showed that tolvaptan decreased the rate of eGFR decline by 0.40 ml/min per 1.73 m² per year (95% CI, 20.25 to 1.05; P=0.23) in patients with CKD1, by 1.13 (95% CI, 0.61–1.66; P=0.001) in those with CKD2, and by 1.66 (95% CI, 0.83–2.45; P=0.001) in those with CKD3, with a trend for a positive subgroup–treatment interaction (P=0.07). Results for patients in CKD3 were similar when split into CKD3a and CKD3b. Tolvaptan treatment effects on eGFR slope were confirmed by comparing the eGFR values before treatment at baseline and those after discontinuation of study drug, which favored tolvaptan across CKD1 through CKD3. Consistent with the beneficial effects of tolvaptan on the rates of eGFR decline, patients with CKD2 and CKD3 randomly assigned to placebo were more likely to progress to a higher CKD stage at the last follow-up visit than those treated with tolvaptan.

This study will be based upon recruitment of an opportunistic sample given the rarity of the condition and the lack of available studies in the setting.

We plan to recruit a total of 150 patients which are currently within reach of the network coordinated by the proponent and composed by 11 Nephrology Centres. This network treats a total of 1500 (already genetically studied) patients of which we expect (based on standard response rates recognized in the population) acceptance to participate in the study to a value of approximately 40% of patients. These will be then allocated to the experimental and control intervention.

The selected sample is adequate to evaluate a significant reduction in the slope of eGFR at 2 years by 10%, which is a clinically relevant piece of information at the current state of knowledge, as well as a complete assessment of the benefits-harms trade-off of the two interventions.

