12.2 Randomization

Randomization process will be carried out by a WEB-based, internet-accessible, system (e-trial platform). Investigators willing to include a patient should log-in into the e-trial platform and complete the registration form.

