12.3 Statistical Methods

A comparative analysis for the primary outcome will be carried out under the principle of "intention-to-treat" and including data from all subjects who are randomized. The efficacy and safety of compared interventions will be assessed. Trial data will be summarized by the calculation of means and standard deviations for normally distributed variables, medians and interquartile ranges for non-normally distributed variables, and frequency and percentage for categorical variables. Missing data will be ignored. The primary and secondary outcomes, namely the slope of the annualized eGFR and TKV will be analyzed using standard statistics including linear mixed-effects models. A P value <0.05 will be deemed significant.There are no plans for interim analyses.

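### No stratification factor and no baseline covariate is specified for the eGFR-slope or htTKV analysis, although the protocol itself treats baseline kidney volume and function as prognostic

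*Combined protocol and SAP*

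**What the plan says.** **Allocation.** Section 12.2 says only: "Randomization process will be carried out by a WEB-based, internet-accessible, system". Section 4.2 adds that the arm is sent online at once without blinding, and Section 4.8 gives the 1:1 ratio. None of the three names a stratification factor, a block scheme or a minimisation rule.

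**Analysis.** Section 12.3 says the slope and TKV will be "analyzed using standard statistics including linear mixed-effects models", with no fixed effects or covariates listed. Section 8.1.1 says the slope will use an appropriate baseline, which is not defined.

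**Population.** Section 5.2 narrows the genotype ("Genetic Diagnosis of Type I ADPKD truncating mutation") but accepts any eGFR of 45 or more.

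**Baseline and outcome.** Section 8.1.2 cites cohort evidence that baseline TKV strongly predicts later GFR loss. Section 3.1 says that TKV, read with age and kidney function, identifies patients at higher risk of progression. Section 12.1 quotes a post hoc analysis by CKD stage of an earlier placebo-controlled tolvaptan trial:
- CKD1: "tolvaptan decreased the rate of eGFR decline by 0.40 ml/min per 1.73 m² per year", with "95% CI, 20.25 to 1.05; P=0.23) in patients with CKD1"
- CKD2: "by 1.13 (95% CI, 0.61–1.66; P=0.001) in those with CKD2"
- CKD3: "by 1.66 (95% CI, 0.83–2.45; P=0.001) in those with CKD3"

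It describes these results "with a trend for a positive subgroup" interaction with treatment (P=0.07).

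**The concern.** The plan identifies two strong baseline predictors and measures both on every patient. Eligibility already rests on the mean of two screening eGFR values (Sections 4.1 and 9.1.6.1). Baseline kidney volume comes from a screening scan or one done within the previous six months (Sections 4.1 and 9.1.1). The plan then assigns neither a role in allocation or analysis.

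Two things are at stake. With about 75 patients per arm, the arms can differ by chance in their mix of CKD stages, and nothing in the plan limits or corrects this. Any part of the slope variation that baseline eGFR or TKV could explain would also stay in the residual. A third consequence follows from the open-label design: if covariates are left open, they can be chosen after results by arm have been seen.

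**Working it through.** **1. What can be reproduced.** The earlier trial's overall reduction in decline is (3.70 - 2.72)/3.70 = 26.5%, as Section 12.1 states. The plan gives no figure for imbalance or for the gain from adjustment.

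**2. How firm the stage figures are.** The lower CKD1 limit prints as 20.25. I read it as -0.25, because (-0.25 + 1.05)/2 = 0.40. The standard error is then 1.30/(2 x 1.96) = 0.332 and z = 0.40/0.332 = 1.21, so P = 0.23, as printed. The CKD3 standard error is (2.45 - 0.83)/(2 x 1.96) = 0.413. The CKD3 minus CKD1 difference is 1.66 - 0.40 = 1.26, with standard error sqrt(0.332² + 0.413²) = 0.530 and 95% CI 0.22 to 2.30. This treats the stages as independent and works from rounded limits. The plan's own interaction test is P=0.07, and the CKD1 interval includes zero.

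**3. Chance imbalance.** Inputs are N = 150 at 1:1 (Sections 4.8 and 12.1), hence 75 per arm. The stage mix is not given, so the share p of a stage is an assumption. Under simple randomisation the SD of the between-arm difference in share is sqrt(2p(1-p)/75).

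| Assumed share p | SD (points) | 95% range (points) | Probability of a difference above 10 points |
|---|---|---|---|
| 0.20 | 6.5 | ±12.8 | 13% |
| 0.33 | 7.7 | ±15.0 | 19% |
| 0.50 | 8.2 | ±16.0 | 22% |

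Example: for p = 0.20, 10/6.53 = 1.53, and the two-sided normal tail is 0.126.

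**4. From imbalance to the slope comparison.** If mean slope differs by g between one stage and the rest, equally in both arms, the arm difference shifts by g times the difference in share. The documents give no g. Assuming g from 0.5 to 2.0 ml/min/1.73 m² per year, the 95% range of the shift runs from ±1.96 x 0.0653 x 0.5 = ±0.06 to ±1.96 x 0.0816 x 2.0 = ±0.32. The plan's 10% target is 0.27 per year taken on 2.72, or 0.37 taken on 3.70. These are illustrations, not estimates for this trial.

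**5. Precision.** If the baseline covariates correlate r with slope, adjustment multiplies the slope variance by about 1 - r². For assumed r = 0.1, 0.3 and 0.5 the factors are 0.99, 0.91 and 0.75. These are equivalent to 150/0.99 = 152, 150/0.91 = 165 and 150/0.75 = 200 patients. The documents give no r.

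**The case against.** The strongest reply is that the plan is silent rather than wrong. It does not say that allocation is unstratified or that baseline eGFR is left out. Baseline eGFR may already enter as the time-zero value, and a random intercept would absorb differences between patients in eGFR level. Randomisation keeps the comparison unbiased on average, and chance imbalance is already reflected in the standard error. All of this stands. It limits the point to what is not specified, and to precision rather than bias. It does not remove the point: a random intercept does nothing for a relation between baseline and slope, which is what Sections 3.1 and 8.1.2 describe.

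A reader might also infer that the tolvaptan effect varies four-fold by stage (1.66/0.40 = 4.15), and that moving 10 points of the tolvaptan arm from CKD1 to CKD3 would change the result by 0.10 x 1.26 = 0.126 per year, a large part of the 0.27 target. The documents do not support this, for three reasons:
- The ratio is between post hoc point estimates, and the smaller one is compatible with zero.
- The figures are tolvaptan-versus-placebo effects, and this trial has no placebo arm. Imbalance acts through each arm's mean slope by stage, which is not given. If untreated decline were 1.26 per year faster in CKD3 than in CKD1, tolvaptan-treated slopes would be equal in the two stages and the shift would change nothing. With other slopes it could be larger or reversed.
- The scenario needs opposite 10-point differences in two stages at once. With an assumed 35/45/20 mix this happens in about 3.5% of simulated trials in either direction, well below the single-stage probabilities.

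**Conclusion.** The concern holds as a gap in specification with a probable cost in precision. No stratification factor and no baseline covariate is named for either the primary or the key secondary endpoint, while the protocol itself calls these baselines prognostic and collects them on everyone. A difference between arms of more than 10 points in the share of one CKD stage has probability of about 13% to 22%, assuming simple 1:1 allocation of 150 patients and stage shares of 20% to 50%. What that does to the slope comparison, and how much precision adjustment would recover, cannot be derived without slopes by stage and the slope SD. Nothing here shows that the planned comparison is biased. The missing sample-size inputs are a separate and larger gap.

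**What to change.** **eGFR model.** Pre-specify baseline eGFR (mean of the two screening values) and log baseline htTKV, each with its interaction with time. A main effect alone adjusts the level and not the slope. Use post-baseline eGFR as the response, so that baseline is not both covariate and outcome. The end-of-run-in value should not serve as the baseline, since it is measured after randomisation and on drug.

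**htTKV.** Analyse month-24 htTKV adjusted for log baseline htTKV. Record scan modality, since Sections 4.1 and 9.1.1 allow the baseline scan to be CT or MRI while follow-up is by CT.

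**Allocation, if enrolment has not begun.** Stratify the web randomisation by screening eGFR (90 or more, 60 to 89, 45 to 59), with concealed, varying block sizes because allocation is open, and include the strata in the models. Keep strata few: crossing three eGFR bands with about 11 sites would give 33 cells, or 150/33 = 4.5 patients per cell. If enrolment has begun, make the model changes alone.

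**Supportive only.** A treatment-by-CKD-stage analysis may be added; it should not carry a conclusion.

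**Cost.** Some SAP wording and, where still possible, a setting in the randomisation platform. No new data are needed.

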- The "on-treatment" period has a duration of two years and, as showed by the TEMPO 3/4 trial (13), tolvaptan seems to be effective only after the first year of treatment;
- The open label extension, the TEMPO 4/4 (20), showed that those patients still on tolvaptan after the first 3 years of treatment had kidney volume growth rate grater than those who received placebo during the first three years of the trial. On the other hand, no advantages were found in terms of eGFR declining rate in those who started tolvaptan later;
- Even if rarely, tolvaptan treatment may cause liver injury, that may virtually increase the risk of MALA;
- Tolvaptan, being an aquaretic drug, may cause dehydration and a virtual increase of the MALA risk;
- Preclinical studies conducted in rodents models of diabetes insipidus induced with tolvaptan, indicate that metformin may significantly interfere with tolvaptan pharmacodynamics, thus limiting its effects.

For all these reasons we can argue that metformin treatment, alone, may be safe and effective in slowing ADPKD progression, at the same extent of tolvaptan. If not, patients not receiving tolvaptan for two years, would not be detrimentally deprived of treatment, as tolvaptan starts to be effective after the first year, and its effects are not additional year by year (20).

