3.1 Primary objectives

Currently, drugs' efficacy in ADPKD has been evaluated by means of eGFR and TKV variations. In ADPKD, kidney function may remain preserved until the 4th to 6th decade of life, when advanced renal cystic involvement has occurred. In fact, measured GFR is a poor marker of disease severity and progression, especially in early phases, when it is preserved through compensatory hyperfiltration during a prolonged period (typically decades), but eventually declines sharply. Despite this, to date, eGFR remains the standard to assess kidney function in randomized clinical trials in ADPKD. By contrast, TKV in relation to age can identify patients with progressive disease. TKV is an accurate estimate of kidney cyst burden and associates with pain, hypertension, gross hematuria, proteinuria or albuminuria, and loss of kidney function. TKV increases exponentially in virtually every ADPKD patient, with an average of 5–6%/year in adults. Elevated TKV, particularly when used together with age and kidney function, identifies individuals who are at higher risk for progression to ESRD. Precise measurement of TKV is necessary in clinical trials to assess the impact of therapeutic interventions over short periods of time and can be obtained by planimetry or stereology analysis of CT images.

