8.1 Effectiveness Endpoints

8.1.1 Primary Endpoint

Primary outcome of the study is to evaluate the *difference between Metformin and Tolvaptan in annualized slope of eGFR (CKD-EPI) for individual subjects*, that will be calculated using an appropriate baseline and post-randomization assessment. Traditionally, the primary endpoint in trials testing renoprotective effects of interventions has been the incidence of ESRD or doubling of serum creatinine, which correlates to a 57% reduction in eGFR. Of note, ADPKD is a relatively slowly progressive disease. In a population such as that of the TEMPO 3:4 trial, which was selected to have early-stage ADPKD (eGFR >60 mL/min), it cannot be expected that this endpoint will occur within the typical duration of a renal trial. Adopting this endpoint would therefore only pick up cases

of acute kidney injury and not be of help for studying the effect of interventions on progression of the disease itself. To stimulate progress in developing renoprotective agents, especially for studies in early-stage CKD and diseases that are relatively slow in progression, the nephrological community has pleaded for the use of alternative endpoints for renal trials, namely lesser declines in eGFR. Regulatory authorities have accepted this proposal. When studying the incidence of a 25% reduction in eGFR [a priori defined in the TEMPO 3:4 trial and accepted by the European Medicines Agency (EMA)], there was a significant 61% relative risk reduction with tolvaptan (number needed to treat to prevent one event was ~11). One of the inclusion criteria for the pivotal TEMPO 3:4 trial was a creatinine clearance as estimated with the Cockroft-Gault equation ≥60 mL/min/1.73 m2. Due to tubular creatinine secretion, creatinine clearance overestimates GFR by ~20%. Consequently, the TEMPO 3:4 trial included a considerable number of ADPKD patients (n = 247; 17%) with an eGFR, as determined by the Chronic Kidney Disease Epidemiology Collaboration (CKD-EPI) equation, of <60 mL/min/1.73 m2. A post hoc analysis indicated that in these patients, treatment efficacy was similar or even slightly better than in those with higher eGFR. However, the number of patients with CKD stage 3b, i.e. an eGFR of 30-45 mL/min/1.73 m2, was small.

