8.1.2 Secondary Endpoints

The key secondary endpoint is *the percent change from baseline in htTKV as measured by CT-scan at 24 months*. The use of htTKV as a surrogate biomarker for progression of ADPKD is supported by the Consortium for Radiologic Imaging Study of Polycystic Kidney Disease (CRISP) which showed that baseline TKV strongly predicts subsequent loss of GFR. TKV is now widely used in RCTs for ADPKD.

Other secondary efficacy end-points include:

- Difference in rate of albuminuria change;

- Difference in rate of urological events and of hypertension onset (for not hypertensive patients at baseline);
- Hypertension worsening or amelioration (for those who are hypertensive);
- Exploratory efficacy Outcomes (changes from baseline in urinary EGF and EGF/MCP-1 levels).

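### 150 patients are called adequate for a 10% slope reduction, but 80% power needs a slope SD of about 0.6–0.8; a non-significant result is therefore likely, and 12.3 names no confidence interval for the conclusion

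*Combined protocol and SAP*

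**What the plan says.** The trial randomises 1:1 to metformin or tolvaptan, with no placebo arm. The primary outcome (8.1.1) is the "difference between Metformin and Tolvaptan in annualized slope of eGFR (CKD-EPI) for individual subjects".

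Section 12.1 describes an opportunistic sample of 150 and states that it is adequate to evaluate a significant 10% reduction in eGFR slope at 2 years. It gives no SD, power, base slope or dropout rate. It does quote an earlier placebo-controlled tolvaptan trial: decline reduced from 3.70 to 2.72 ml/min/1.73 m² per year, with stage-specific effects of 0.40, 1.13 and 1.66 and their confidence intervals.

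Section 12.3 says that the slope and TKV outcomes "will be analyzed using standard statistics including linear mixed-effects models", and then: "A P value <0.05 will be deemed significant". It sets no margin, confidence-interval rule or reading of a non-significant result. Section 3.1, headed as the primary objectives, states no hypothesis.

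The rationale in 2.2.2 argues that "metformin treatment, alone, may be safe and effective in slowing ADPKD progression, at the same extent of tolvaptan".

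**The concern.** The adequacy statement in 12.1 is the only justification of the sample size, and it cannot be reproduced from what the plan gives. If it is far off, the trial will probably end with P≥0.05 even if a true 10% difference exists. It will also end that way in 95% of trials if the two drugs are equally effective. That 95% is only the definition of the significance level. It matters here because equality is what the rationale suggests, and because without placebo a null result cannot distinguish two active drugs from two inactive ones.

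What is at stake is the conclusion the trial can support. A P value alone does not show which losses of effect have been excluded. The mixed models named in 12.3 would yield an estimate and a standard error, but the plan does not make them the basis for the conclusion.

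**Working it through.** **Inputs.** From the plan: 150 patients at 1:1, so n = 75 per arm; significance level 0.05; slopes 3.70 and 2.72, hence a tolvaptan effect of 3.70 − 2.72 = 0.98. Assumed: a two-sided test (sidedness is not stated), all 150 analysed, and the SD. Section 12.3 ignores missing data, so 75 per arm is a best case.

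**The plan's own figure.** The claim that 150 is adequate cannot be reproduced without an SD and a power, so I solved for the SD.
- 10% reduction: 0.1 × 2.72 = 0.272, or 0.1 × 3.70 = 0.37.
- SD for 80% power = d / (2.8016 × √(2/75)), with √(2/75) = 0.1633.
- 0.272 / 0.4575 = 0.59; 0.37 / 0.4575 = 0.81.
- With a one-sided 0.05 test the values would be 0.67 and 0.91.

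**A rough SD from the plan's own intervals.**
- CKD3 effect in 12.1: SE = (2.45 − 0.83) / 3.92 = 0.413. Section 8.1.1 says the earlier trial "included a considerable number of ADPKD patients (n = 247; 17%) with an eGFR" below 60. If those 247 are the CKD3 group, the SD is 3.25 at 1:1 or 3.06 at 2:1 allocation (split assumed).
- Pooling the three stage intervals, with the garbled CKD1 limit read as −0.25, gives SE 0.186. With N = 247 / 0.17 = 1453, the SD is 3.55 or 3.34.

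This treats model-based standard errors from another population and duration as simple two-sample ones. I therefore use 3.0–3.6 as a rough range and show lower values beside it.

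**Results at 75 per arm** (noncentral t; half-width = 1.976 × SD × 0.1633):

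| SD (assumed) | 95% CI half-width | Power, 0.272 | Power, 0.37 | P≥0.05 if true difference is 0.98 |
|---|---|---|---|---|
| 1.0 | 0.32 | 38% | 62% | <1% |
| 1.5 | 0.48 | 20% | 32% | 2% |
| 2.0 | 0.65 | 13% | 20% | 15% |
| 2.5 | 0.81 | 10% | 15% | 34% |
| 3.0 | 0.97 | 9% | 12% | 49% |
| 3.6 | 1.16 | 7.5% | 10% | 62% |

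At SD 1.5 a true 10% difference is missed in 68–80% of trials, and at higher SDs more often.

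**Dependence on the true effect.** The last column takes metformin as inactive and tolvaptan as delivering 0.98. For the stage-specific effects in 12.1, the chance of P≥0.05 at SD 3.0–3.6 is 87–90% (0.40), 37–52% (1.13) and 8–20% (1.66). Section 2.2.2 also says that "tolvaptan seems to be effective only after the first year of treatment". Take no effect in year 1, a constant effect afterwards and a 3-year average of 0.98. The difference visible over 2 years is then 0.98 × 3/2 ÷ 2 = 0.735 end to end, or 0.98 × 0.5/0.741 = 0.66 by least squares. The chance of P≥0.05 becomes 38–48% at SD 2.0 and 68–80% at SD 3.0–3.6.

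**The case against.** The strongest reply is that this is a difference trial. The endpoint, the 10% target and the P<0.05 criterion all say so. The sentence about equal effect is hedged background explaining why the drugs are not combined, and no section sets a comparability hypothesis. That stands. A reader might infer that the sponsor means to present non-significance as equivalence, or that a non-inferiority margin is missing from a trial that needs one. The documents support neither inference. The reply does not rescue 12.1, however, because the shortfall in power arises under the difference aim itself.

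A reader might also infer that P≥0.05 would be uninformative unless the SD were well below 2. The figures do not bear this out for loss of the whole effect: at SD 2.0 the trial has about 85% power against a true difference of 0.98.

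The SD of 3.0–3.6 is fragile, for the reasons given with its derivation. The 49–62% range is conditional on 0.98 and should not be quoted as a firm property of the trial. Eligibility starts at an eGFR of 45, the stage mix is unknown, and the plan selects faster progressors, in whom it expects a larger tolvaptan benefit. The power shortfall does not depend on that range: power for the 10% target is already below 80% at SD 1.0.

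Finally, the key secondary endpoint, "the percent change from baseline in htTKV as measured by CT-scan at 24 months", could be set against the statement in 3.1 that "TKV increases exponentially in virtually every ADPKD patient, with an average of 5–6%/year in adults". That comparison is indirect and historical, and does not settle the eGFR question.

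**Conclusion.** The concern holds in this form. The adequacy claim in 12.1 is true only if the slope SD is about 0.6–0.8. Power for the 10% target is 38–62% at SD 1.0, 13–20% at 2.0 and about 8–12% at 3.0–3.6. A non-significant result is the likely outcome under that target at any SD from 1.5 up, and also under equal efficacy.

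The plan does not misread such a result, but it names no confidence interval from which to draw the conclusion. How much P≥0.05 would say about losing the whole tolvaptan effect cannot be settled from the documents. For a true difference of 0.98 the loss is missed in about 15% of trials at SD 2.0 and 49–62% at SD 3.0–3.6, with wide variation over effects of 0.40–1.66.

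These figures rest on a two-sided test, 75 analysed per arm and assumed SDs. The analysis is not invalid; the sample-size claim is unsupported and the rule for concluding is incomplete.

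**What to change.** 1. **Section 12.1.** State the SD, its source and the base slope for the 10%. Replace the adequacy claim with the power, or the 95% CI half-width, that 75 per arm delivers.
2. **Section 12.3.** Make the metformin-minus-tolvaptan slope difference with its two-sided 95% CI the primary result, and state that P≥0.05 alone will not be reported as similar efficacy.
3. **Only if a comparability claim is wanted.** Before data are seen, the sponsor should state and justify a margin and a reading rule that covers every position of the CI, including one lying wholly beyond the margin. It should also say that, without placebo, the claim rests on tolvaptan's historical effect holding in this population over 2 years, which the trial cannot check.

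**Cost.** Items 1 and 2 take a few sentences and need no extra patients, visits or data. They add no power. The downside is that the stated adequacy becomes less favourable and the plan admits that an inconclusive result is likely.

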1. SYNOPSIS	
TITLE	Metformin versus Tolvaptan in adults with Autosomal Dominant Polycystic Kidney Disease (ADPKD): a phase 3a, independent, multi-centre, 2 parallel arms randomized controlled trial
SPONSOR	Università degli Studi di Bari Dipartimento dell'Emergenza e dei Trapianti di organi (D.E.T.O.)
PHASE	III
RATIONALE	Autosomal dominant polycystic kidney disease (ADPKD) is the most common inherited renal disorder occurring in 1:400–1:1.000 live births. It affects 4 to 6 million persons worldwide and about 205.000 people in Europe (EU). This figure is equivalent to 4 in 10.000 people and thus below the prevalence threshold of 5 in 10.000 used to designate a disease as rare in EU. Renal cyst development and expansion in ADPKD involves both fluid secretion and abnormal proliferation of cyst-lining epithelial cells. The chloride channel of the cystic fibrosis transmembrane conductance regulator (CFTR) participates in secretion of cyst fluid, and the mammalian target of rapamycin (mTOR) pathway may drive proliferation of cyst epithelial cells. CFTR and mTOR are both negatively regulated by AMP-activated protein kinase (AMPK). Metformin, a drug widely used, is a pharmacological activator of AMPK. We found that metformin stimulates AMPK, resulting in inhibition of both CFTR and the mTOR pathways. Metformin induces significant arrest of cystic growth in both in vitro and ex vivo models of renal cystogenesis. In addition, metformin administration produces a significant decrease in the cystic index in two mouse models of ADPKD. These results suggest a possible role for AMPK activation in slowing renal cystogenesis as well as the potential for therapeutic application of metformin in the context of ADPKD
OBJECTIVES	Objective of the study is to assess if a two-year course of 1500 mg oral metformin is effective and safe in treatment of ADPKD, as compared to the actual gold-standard therapy, tolvaptan (Jinarc®)
ENDPOINTS	 Primary outcome of the study is to evaluate the difference between Metformin and Tolvaptan in annualized slope of eGFR (CKD-EPI) for individual subjects, that will be calculated using an appropriate baseline and post-randomization assessment. The key secondary endpoint is the percent change from baseline in htTKV as measured by CT-scan at 24 months. The safety endpoin include: changes from baseline in creatinine; vital signs; laboratory values including liver function tests, rate

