3. OBJECTIVES

Objective of the study is to assess if a two-year course of 1500 mg oral metformin is effective and safe in treatment of ADPKD, as compared to the actual gold-standard therapy, tolvaptan (Jinarc®).

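### Section 12.3 sets an unadjusted P<0.05 for primary and secondary outcomes without tying claims to the protocol's own ranking; for the two outcomes it names, the false-claim rate is about 10%

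*Combined protocol and SAP*

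**What the plan says.** The analysis rule is in section 12.3. It first states: "The primary and secondary outcomes, namely the slope of the annualized eGFR and TKV will be analyzed using standard statistics including linear mixed-effects models". It then adds: "A P value <0.05 will be deemed significant". The sidedness of the test is not given, and no interim analysis is planned.

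The endpoints are ranked elsewhere:

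- **Primary** (Synopsis and 8.1.1): "Primary outcome of the study is to evaluate the difference between Metformin and Tolvaptan in annualized slope of eGFR (CKD-EPI) for individual subjects".
- **Key secondary** (Synopsis and 8.1.2): "The key secondary endpoint is the percent change from baseline in htTKV as measured by CT-scan at 24 months". Section 3.2 also makes TKV the main secondary objective.
- **Further outcomes** (8.1.2), introduced by "Other secondary efficacy end-points include". The list covers how fast albuminuria changes; urological events together with new hypertension, in one compound bullet; and change in hypertension among patients who already have it.
- **Exploratory** (8.1.2, last bullet of the same list): urinary EGF and EGF/MCP-1.

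The objective in section 3 is to find out whether metformin "is effective and safe in treatment of ADPKD, as compared to the actual gold-standard therapy". It is not tied to a particular endpoint. The documents contain no testing order, split of alpha, multiplicity adjustment, or statement that the lower-ranked outcomes are descriptive.

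**The concern.** Labels such as primary and key secondary say which outcome matters most. They do not say what may be concluded when the primary misses and a secondary hits. Under the 12.3 rule, htTKV at P<0.05 is significant whether or not the eGFR slope is.

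The protocol's own text makes that outcome easy to argue from. Section 3.1, headed as the primary objectives, does not state which measure decides success. It describes GFR as a weak marker in early disease and TKV as necessary for judging interventions over short periods, although it also calls eGFR the standard in randomized ADPKD trials. A two-year trial that missed on slope could therefore rest its conclusion on TKV without departing from the written plan.

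What is at stake is the error rate of a claimed difference between metformin and tolvaptan. The 5% applies to one pre-named comparison, not to whichever of several comparisons reaches 0.05.

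**Working it through.** The documents give no familywise error rate to reproduce. The only stated figure is the per-test threshold of 0.05.

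**Inputs**

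- Alpha per test: 0.05 (12.3). Two-sided is my assumption, because sidedness is not stated.
- Number of looks: one (12.3 plans no interim analyses).
- Number of outcomes, k:
  - k = 1: the eGFR slope alone.
  - k = 2: the outcomes named in 12.3, eGFR slope and TKV.
  - k = 6: these two plus albuminuria, urological events, hypertension onset, and hypertension worsening or amelioration (8.1.2, with the compound bullet split).
  - k = 8: the six plus urinary EGF and EGF/MCP-1, which 8.1.2 labels exploratory.

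**Formulas**, for no true difference on any outcome:

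- Independent tests: P(at least one P<0.05) = 1 − (1 − 0.05)^k
- Upper bound under any dependence: k × 0.05
- False findings in metformin's favour only, independent tests: 1 − (1 − 0.025)^k

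**Results**

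| k | Independent, either direction | Bound | Independent, metformin's favour only |
|---|---|---|---|
| 1 | 5.0% | 5% | 2.5% |
| 2 | 1 − 0.95² = 9.75% | 10% | 1 − 0.975² = 4.9% |
| 6 | 1 − 0.95⁶ = 26.5% | 30% | 1 − 0.975⁶ = 14.1% |
| 8 | 1 − 0.95⁸ = 33.7% | 40% | 1 − 0.975⁸ = 18.3% |

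**Correlation.** A simulation of eight equally correlated two-sided z-tests (1,000,000 replicates) gives the following chance of at least one P<0.05:

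| Assumed correlation | Eight outcomes |
|---|---|
| 0.2 | 31.9% |
| 0.3 | 30.0% |
| 0.5 | 25.0% |
| 0.8 | 15.7% |

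The documents give no correlations, so these are assumed values. Some positive correlation is plausible: 8.1.2 reports that baseline TKV predicts GFR loss, 3.1 links TKV to hypertension and albuminuria, and EGF is part of the EGF/MCP-1 measure.

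**With a fixed sequence.** If htTKV is tested only after a significant slope comparison, and no other efficacy outcome carries a significance claim, the chance of any false claim is at most 5%. A Bonferroni split over eight tests (0.05/8 = 0.00625 each) would also hold it, at 1 − (1 − 0.00625)^8 = 4.9%, but it would cut the threshold for the primary comparison, which the sequence does not.

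**The case against.** The strongest reply is that the hierarchy already exists. There is one primary outcome, one key secondary, a list of other secondary outcomes and an exploratory pair, and the adequacy statement in 12.1 refers to the eGFR slope alone. A conventional reader would base the conclusion on the slope and treat the rest as supportive. Section 12.3 also names only eGFR slope and TKV.

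Much of this stands. The primary comparison keeps its 5% rate, and the two renal measures are not co-equal. A reader might infer from the flat rule that the plan carries a one-in-three chance of a false efficacy claim. The documents do not support that, for these reasons:

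- Applying P<0.05 to all eight outcomes is an inference from a general sentence; 12.3 names two.
- Two of the eight are labelled exploratory.
- Nowhere do the documents say that a win on any listed outcome establishes efficacy.
- The 33.7% counts differences in either direction. In metformin's favour only, it is 18.3%.
- The 33.7% is the value under independence, not a ceiling. Positive correlation of the kind simulated lowers it, and the bound under any dependence is 40%.

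What the reply does not remove is the gap between ranking endpoints and ranking claims. Section 12.3 calls a TKV result below 0.05 significant regardless of the slope, and no other section limits how that may be used.

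**Conclusion.** The point holds in a limited form. Section 12.3 does not say that claims follow the protocol's own ranking. If a significant result on either outcome it names counts as a claim of a treatment difference, the false-claim rate is about 10% rather than 5%: 9.75% if the tests are independent, 10% at most. This assumes two-sided tests and no true difference on either outcome.

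The larger figures, 26.5% for six outcomes and 33.7% for eight, need three further conditions: each outcome tested at two-sided 0.05, independence, and any single result accepted as a claim. They describe what the wording leaves open, not what the plan commits to.

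This is a cheap improvement to the text, not a flaw in the primary test.

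**What to change.** Replace the significance sentence in 12.3 with:

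> A claim of a difference in efficacy between the arms rests on the eGFR-slope comparison at two-sided 0.05. Percent change in htTKV at 24 months is tested at two-sided 0.05 only if that comparison is significant. All other efficacy outcomes are reported with 95% confidence intervals and without significance claims. Safety reporting is unaffected.

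This uses the ranking the protocol already has and states the sidedness. It needs no extra patients, visits or data.

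The cost is that htTKV can serve only as supportive evidence if the slope comparison misses 0.05, however small its own P value.

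The wording speaks of a difference between arms on purpose. Section 2.2.2 argues that metformin may slow progression as much as tolvaptan does. Whether similar performance would count as effective is a separate question that this text does not settle, and the change should not be read as defining effectiveness as superiority over tolvaptan.
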